## 6. STUDY DRUG

### 6.1 Description of Investigational Agents

#### **Ixazomib Capsules**

The ixazomib drug product is provided in strengths of 4.0-, 3.0-, and 2.3-mg capsules as the active boronic acid. The different dose strengths are differentiated by both capsule size and color as described below:

Dose Strength	Capsule Size	Capsule Color
4.0 mg	Size 4	Ivory
3.0 mg	Size 3	Light gray
2.3 mg	Size 2	Light pink

For additional details, please see the ixazomib IB.

### 6.2 Study Drug Administration

#### **Cycles 1-12 (28-day cycle)**

- Ixazomib 4 mg PO on Days 1, 8, and 15 (3 mg if CrCl < 30 mL/min)
- Rituximab 375mg/m^2 IV weekly for the first 4 weeks in cycle 1, and starting cycle 3, Rituximab 375mg/m^2 IV will be given on Day 1 of each cycle. Total of 12 cycles will be given.

Patients benefiting from the clinical trial will continue with Ixazomib indefinitely until patient withdraws consent, disease progression or unacceptable toxicity.

#### Ixazomib Administration

All protocol-specific criteria for administration of study drug must be met and documented before drug administration. Study drug will be administered or dispensed only to eligible patients under the supervision of the investigator or identified subinvestigator(s). Patients should be monitored for toxicity, as necessary, and doses of ixazomib should be modified as

needed to accommodate patient tolerance to treatment; this may include symptomatic treatment, dose interruptions, and adjustments of ixazomib dose (see Section 6.3).

Capsules of ixazomib will also be referred to as study drug. Study drug will be supplied by Millennium as capsules of 2.3-, 3.0- and 4.0 mg ixazomib.

The prescribed administration of ixazomib doses in this study is 4 mg ixazomib in a 28 day cycle.

Patients should be instructed to swallow ixazomib capsules whole, with water, and not to break, chew, or open the capsules. Ixazomib should be taken on an empty stomach (no food or drink) at least 1 hour before or at least 2 hours after food. Each capsule should be swallowed separately with a sip of water. A total of approximately 8 ounces (240 mL) of water should be taken with the capsules.

Missed doses can be taken as soon as the patient remembers if the next scheduled dose is 72 hours or more away. A double dose should not be taken to make up for a missed dose. If the patient vomits after taking a dose, the patient should not repeat the dose but should resume dosing at the time of the next scheduled dose.

#### Ixazomib Destruction

Investigational ixazomib (expired or end of study) should be destroyed on site according to the institution's standard operating procedure. Be sure to document removal and destruction on drug accountability logs.

#### Rituximab Administration

Pre-medication consisting of acetaminophen and diphenhydramine should be considered before each infusion of rituximab to attenuate potential infusion reactions. Since transient hypotension may occur during rituximab infusion, consideration should be given to withholding antihypertensive medications 12 hours prior to rituximab infusion.

Rituximab First Infusion\*: The Rituximab solution for infusion should be administered intravenously at an initial rate of 50 mg/hr. Rituximab should not be mixed or diluted with other drugs. If hypersensitivity or infusion related events do not occur, the infusion can be escalated to 50 mg/hr increments every 30 minutes, to a maximum of 400 mg/hr. If hypersensitivity or an

infusion- related event develops, the infusion should be temporarily slowed or interrupted. The infusion can continue at one-half the previous rate upon improvement of patient symptoms.

Subsequent Rituximab Infusions: Subsequent Rituximab infusions can be administered at an initial rate of 100 mg/hr, and increased by 100 mg/hr increments at 30 minute intervals, to a maximum of 400 mg/hr as tolerated.

\*Patients with peripheral blood involvement (leukemic presentation) as defined for this purpose as  $> 20,000$  lymphocytes per  $\text{mm}^3$  as determined by flow cytometry studies, rituximab will NOT be initiated on Day 1. In this case, ixazomib will be started alone. Rituximab may be initiated on the next cycle if the lymphocyte count drops to  $< 20,000/\text{mm}^3$  in peripheral blood. For such patients, or for those with high tumor burden, despite lymphocyte count  $< 20,000$  cells/ $\text{mm}^3$  (as determined by the principal investigator), infusion of rituximab may be abbreviated as outlined below. If the patient progresses despite one cycle of ixazomib, the patient will be taken off protocol.

Day 1 – Rituximab 50 mg/ $\text{m}^2$

Day 2 – If no cytokine release phenomenon is noted on Day 1 and the peripheral blood white cell counts have decreased to  $< 20,000$  cells/ $\text{mm}^3$  or  $< 25\%$  of base line WBC counts, then the dose of rituximab can be increased to 325 mg/ $\text{m}^2$  on Day 2 at PI discretion.

A similar 2-day split dose approach may be taken for rituximab infusion on Days 8, 15 and 22 in patients with high tumor burden or high peripheral blood WBC counts as determined by the PI prior to each infusion of rituximab. If initiation of rituximab is delayed until Cycle 2, it will be followed by rituximab on day one of every cycle starting in Cycles 4 – 8.

Please refer to rituximab package insert for details concerning drug storage, preparation and administration guidelines.

All rituximab infusions will be administered at MD Anderson.

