## **4. STUDY DESIGN**

### **4.1 Overview of Study Design**

Open label, single center, single –arm, phase II testing the combination of ixazomib and rituximab in the treatment of subjects with relapsed or refractory MCL. The study will enroll 24 patients. The treatment plan starts with oral ixazomib at the US approved dose of 4 mg. All subjects will have disease restaging at 8 weeks. Rituximab IV will be given once weekly for the first 4 weeks. Rituximab IV will restart at cycle 3, and continue monthly until cycle 12.

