**Special Attention**

Patients who wish to continue with ixazomib after completion of week 56 can continue on with therapy with ixazomib single agent. Rituximab will not be continued post week 56.

End of study biopsy and MRD testing is required.

Medications	C1D1	C1D8	C1D15	C1D21	C2 and Beyond
Rituximab	X	X	X	X	Rituxan to continue C3D1, with each cycle D1
Ixazomib	X	X	X		Continue days 1, 8 and 15 of each cycle.
TLS Assessment A	X	X	X	X	Continue days 1, 8 and 15 of each cycle.
Physical Exam	X				
CBC	X	X	X	X	
CMP	X	X	X	X	

- A. Patients should be assessed for risk and should receive appropriate prophylaxis for TLS, including hydration and anti-hyperuricemics. Monitor blood chemistries and manage abnormalities promptly. Interrupt dosing if needed. Employ more intensive measures (intravenous hydration, frequent monitoring, hospitalization) as overall risk increases

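### As printed, the delayed-start rule ends rituximab at Cycle 8 in leukemic patients (9 infusions against 13 for a plain one-cycle shift), with no reason given and the weekly course left unplaced

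*Combined protocol and SAP*

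**What the plan says.** Standard schedule. Section 6.2 gives rituximab "weekly for the first 4 weeks in cycle 1, and starting cycle 3" on Day 1 of each cycle, and adds "Total of 12 cycles will be given". Section 4.1 agrees on the end: "Rituximab IV will restart at cycle 3, and continue monthly until cycle 12".

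Delayed start. Under Rituximab Administration in section 6.2, a patient with more than 20,000 lymphocytes/mm³ gets no rituximab on Day 1 and starts ixazomib alone. Then "Rituximab may be initiated on the next cycle if the lymphocyte count drops to" below that level. If the start is put back to Cycle 2, "it will be followed by rituximab on day one of every cycle starting in Cycles 4 – 8". The sentence just before allows split dosing on Days 8, 15 and 22 in patients with high tumor burden or high white counts. Nothing says whether the four weekly infusions move to Cycle 2.

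Schedule tables. The medication table in section 11.3 (Special Attention) covers only a Cycle 1 start: "Rituxan to continue C3D1, with each cycle D1". The same part says "Rituximab will not be continued post week 56".

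Analysis set. Section 7.1 measures all endpoints in everyone with at least one dose of study drug, and section 6.2 states "Capsules of ixazomib will also be referred to as study drug". Delayed starters therefore count in every endpoint from their first capsule.

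**The concern.** The delayed-start sentence is the only instruction for a defined group of patients, and it departs from the standard course in two ways. Its printed range ends at Cycle 8 where the standard course ends at Cycle 12, and it does not place the weekly course. The delay has a clear reason, the leukemic presentation and the risk of cytokine release. The earlier end has none.

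Rituximab is one of the two drugs under test. A clinician who follows the sentence as printed would stop it four cycles early in patients with peripheral blood involvement. A clinician who treats it as the standard course moved by one cycle would not. The same patient could be treated differently under the same protocol, and the results after that point would mix the two courses.

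**Working it through.** The plan states no infusion counts, so there is no figure to reproduce. The counts below come from the schedule.

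Inputs: 28-day cycles (section 6.4.1); primary assessment at week 16 (section 7.1), which is day 112 = 4 × 28, the end of Cycle 4; PET/CT at the end of Cycle 4 (section 11.3, footnote F). The Cycle 4 Day 1 infusion therefore falls before the primary assessment and the Cycle 5 one after it. A two-day split counts as one infusion.

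Day 1 doses: Cycles 3 to 12 = 10; Cycles 4 to 8 = 5; Cycles 4 to 12 = 9.

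| Reading | By week 16 | In all |
|---|---|---|
| Cycle 1 start, to Cycle 12 | 4 + 2 = 6 | 4 + 10 = 14 |
| Cycle 2 start, weekly course moved, to Cycle 8 (as printed) | 4 + 1 = 5 | 4 + 5 = 9 |
| Cycle 2 start, weekly course moved, to Cycle 12 | 4 + 1 = 5 | 4 + 9 = 13 |
| Cycle 2 start, one dose in Cycle 2, to Cycle 8 | 1 + 1 = 2 | 1 + 5 = 6 |
| Cycle 2 start, one dose in Cycle 2, to Cycle 12 | 1 + 1 = 2 | 1 + 9 = 10 |

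Which Cycle 2 reading is likelier? Three features of the text favor the weekly course moving:

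- The protocol speaks of delaying the initiation of rituximab, which puts back a course and does not replace it with one dose.
- The standard pattern is a weekly cycle, a skipped cycle, then Day 1 dosing. Cycle 2, nothing in Cycle 3, then Day 1 from Cycle 4 is the same pattern one cycle later. Skipping Cycle 3 after a single dose would make little sense.
- The adjacent sentence mentions Days 8, 15 and 22 for patients with high counts. It could also apply to Cycle 1 starters, so it supports this reading without settling it.

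Against it, the dosing text ties the weekly infusions to Cycle 1.

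On the likelier reading, the one-cycle delay costs 6 − 5 = 1 infusion by week 16 and 14 − 13 = 1 in all. The Cycle 8 end costs a further 13 − 9 = 4 (Cycles 9 to 12). The first of these would fall on day 8 × 28 + 1 = 225, after week 32. As printed, a delayed starter gets 9/14 = 64% of the standard number.

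End of the course: Cycle 12 ends at 12 × 28 = 336 days, week 48. Week 56 is 392 days, the end of Cycle 14. The 11.3 table gives no last cycle, so a reader who takes week 56 as the end would give a Cycle 1 starter 4 + 12 = 16 infusions, not 14.

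**The case against.** The best defense is that the sentence is merely clumsy. It combines a start with a range, so Cycle 8 may not be meant as an end. If Day 1 dosing runs to Cycle 12, a delayed starter gets 13 infusions against 14, and only the delay remains. The week-56 statement can be read as a ceiling that orders no dosing beyond Cycle 12.

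Part of this stands. The text does not prove that a shorter course was intended, and the week-56 limit is loose more than contradictory. But Cycle 8 is the only later cycle number given for these patients, and no other section overrides it. A dosing instruction should not depend on the reader deciding that its printed range is a slip.

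A reader might infer something stronger: that leukemic patients get 2 infusions against 6 by week 16, and that the primary CR rate is lowered as a result. The documents do not support this. The count of 2 requires the weekly course to disappear, which is the less plausible reading. On the likelier one the count is 5 against 6, and the corrected rule also gives 5, so it leaves exposure at the primary assessment unchanged. The four infusions at issue fall after week 16. The documents also give neither the number of delayed starters nor any relation between rituximab dose and CR.

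**Conclusion.** The point holds as a fault in a dosing rule. Followed as printed, with the weekly course moved to Cycle 2, it stops rituximab four cycles early in leukemic patients: 9 infusions against 13 for a simple one-cycle shift and 14 for a Cycle 1 start. The Cycle 8 end is unexplained; the delay itself is not at fault.

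The main effect is on later treatment, and so on PFS, OS and response after week 16. The size is stated per patient, because the number of delayed starters is not given, and no size can be put on the effect on outcomes. The figures assume that Cycle 8 is the last cycle and that the weekly course moves. The wording should also rule out the literal alternative, 2 infusions by week 16 and 6 in all.

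**What to change.** Replace the delayed-start sentence in section 6.2 with: *If rituximab starts in Cycle 2, give it on Days 1, 8, 15 and 22 of Cycle 2, then on Day 1 of Cycles 4 to 12.* Add a matching footnote to the medication table in section 11.3, and change the week-56 limit there to agree with Cycle 12. If ending at Cycle 8 is deliberate, keep it but state the reason and place the weekly course.

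The cost is 4 more infusions per delayed starter (Cycles 9 to 12). Against the most literal reading it is up to 13 − 6 = 7, with 3 more weekly infusions in Cycle 2. These are infusions that the standard course already includes. Sample size, endpoints and analyses do not change.

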### 6.3 Risk for TLS

#### 6.3.1 High Risk for TLS:

High risk for TLS – Subjects with high tumor burden (at least one lesion >10 cm; or at least one lesion >5 cm and lymphocyte count >25,000 cells/mm^3) and/or with baseline creatinine clearance (CrCl) <80 mL/min.

- o Subjects at high risk for TLS will be hospitalized for a minimum of 24 hours (and up to 48 hours at the discretion of the investigator) after the first dose of ixazomib for monitoring and prophylaxis of TLS.
- o During hospitalization of the first dose for high risk pts, Blood Chemistries should be analyzed at baseline, between 4-8 hours, 12-24 hours after administration of the drug for signs of electrolyte changes. The 24 blood chemistries should be analyzed for signs of TLS prior to administering next dose of ixazomib.
- o Patients should receive oral hydration of 1.5 – 2 liters of fluid and 150 – 200 m/hr as tolerated. Start allopurinol or xanthine oxidase inhibitor 2 to 3 days prior to initiation of therapy and rasburicase if baseline uric acid is elevated.
- o Pre-dose blood chemistries at each step up dose of ixazomib and correct any blood chemistry abnormalities.
- o For high-risk patients, outpatient monitoring should occur at next dose pre-dose, 6-8 hour and 24 hours. The next dose should not be administered until the 24 hour labs are examined for signs of TLS

#### 6.3.2 Medium Risk for TLS

Any lymph node 5 cm to <10 cm OR lymphocyte count  $\geq 25 \times 10^9/L$

- o Patients should receive oral hydration of 1.5 – 2 liters of fluid and start allopurinol or xanthine oxidase inhibitor 2 to 3 days prior to initiation of therapy and consider additional intravenous fluids.
- o Pre-dose blood chemistries at each step up dose of ixazomib and correct any blood chemistry abnormalities.
- o Medium risk patients should have outpatient monitoring of blood chemistries for the 1st dose of ixazomib. Monitoring should occur at baseline, 6-8 hours and 24 hours. The next dose should not be administered until the 24 hour lab results are examined for signs of TLS. Subsequent doses require a pre-dose blood chemistry assessment.

#### 6.3.3 Low Risk for TLS

All others not meeting the criteria for high risk for TLS.

- o Patients should receive oral hydration of 1.5 – 2 liters of fluid and start allopurinol or xanthine oxidase inhibitor 2 to 3 days prior to initiation of therapy if uric acid levels are

above normal reference range.

- o Pre-dose blood chemistries at each dose of ixazomib and correct any blood chemistry abnormalities.
- o Low risk pts should have outpatient monitoring of blood chemistries for the 1st dose of ixazomib. Monitoring should occur at baseline. If abnormal renal function ( $Cr > 1.4$ ) or above normal range on uric acid. Should repeat complete metabolic panel (CMP) in 24 hours to make sure no biochemical evidence of tumor lysis.

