## 5. STUDY POPULATION

### 5.1 Inclusion Criteria

Each patient must meet all of the following inclusion criteria to be enrolled in the study:

1. Male or female patients 18 years or older.
2. Patients must have histologically confirmed diagnosis of Mantle Cell Lymphoma.
3. Patients must have measurable disease, as defined by at least one of the following:
  - Lymph node or mass 2 cm or greater, splenomegaly > 13 cm
  - Bone marrow only disease as per morphology or flow cytometry
4. Patients must have relapsed and/or refractory disease to at least 2 lines of therapy including either an anthracycline- or bendamustine- based regimen and a BTK inhibitor.
5. Patients must have an Eastern Cooperative Oncology Group (ECOG) performance status and/or other performance status 0, 1, or 2.
6. Patients must have normal organ and marrow function as defined below:
  - a. Absolute neutrophil count (ANC)  $\geq 1,000/\text{mm}^3$
  - b. Platelets  $\geq 50,000/\text{mm}^3$
  - c. Total bilirubin  $< 1.5 \times$  institutional upper limit of normal (ULN). In patients with documented Gilbert's syndrome, total bilirubin  $\leq 2.5 \times$  ULN.
  - d. AST (SGOT)/ALT(SGPT)  $\leq 3 \times$  ULN
  - e. Creatinine clearance  $\geq 30$  mL/min (See Appendix 11.2)
7. Patients must be willing to give written consent before performance of any study related procedures not part of standard medical care, with the understanding that consent may be withdrawn by the patient at any time without prejudice to future medical care.
8. Female patients who:

- Are postmenopausal for at least 1 year before the screening visit, OR
  - Are surgically sterile, OR
  - If they are of childbearing potential, agree to practice 2 effective methods of contraception, at the same time, from the time of signing the informed consent form through 90 days after the last dose of study drug OR,
  - Agree to practice true abstinence when this is in line with the preferred and usual lifestyle of the patient. (Periodic abstinence [e.g., calendar, ovulation, symptothermal, post-ovulation methods] and withdrawal are not acceptable methods of contraception.)
9. Male patients, even if surgically sterilized (i.e., status post-vasectomy), must agree to one of the following:
- Agree to practice effective barrier contraception during the entire study treatment period and through 90 days after the last dose of study drug OR,

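### The TLS risk tiers in section 6.3 overlap, drop some 5 to 10 cm lesions into Low, and tie a High-risk chemistry check to a dose step-up that never happens

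*Combined protocol and SAP*

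**What the plan says.** Section 6.3.1 places a patient in High for "at least one lesion >10 cm; or at least one lesion >5 cm and lymphocyte count" above 25,000/mm³, and/or a baseline creatinine clearance (CrCl) below 80 mL/min. Section 6.3.2 defines Medium as "Any lymph node 5 cm to <10 cm OR lymphocyte count" of at least 25 × 10⁹/L. Section 6.3.3 defines Low as "All others not meeting the criteria for high risk for TLS".

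The pre-dose chemistry rules differ by tier:

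- **High:** "Pre-dose blood chemistries at each step up dose of ixazomib", plus first-dose monitoring in hospital and, for the second dose, "For high-risk patients, outpatient monitoring should occur at next dose pre-dose, 6-8 hour and 24 hours".
- **Medium:** the same step-up bullet, repaired by a later sentence: "Subsequent doses require a pre-dose blood chemistry assessment".
- **Low:** "Pre-dose blood chemistries at each dose of ixazomib".

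Section 6.2 sets ixazomib at 4 mg on Days 1, 8 and 15 of each 28-day cycle. Table 6-1 lists only reductions (3.0 mg, 2.3 mg, stop), and the text after Table 6-3 rules out raising a dose once it has been lowered. Inclusion criterion 3 in section 5.1 accepts "Lymph node or mass 2 cm or greater" as measurable disease.

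**The concern.** Three things look wrong.

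1. Low is written as the complement of High alone, so a Medium patient who is not High also satisfies it.
2. Even if Low is read as the remainder, the cut-points do not meet. High refers to lesions and needs more than 10 cm. Medium refers to lymph nodes and stops short of 10 cm.
3. The step-up trigger has nothing to act on under flat dosing. Medium and Low have another rule for later doses; High does not.

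The tier decides first-dose protection. Medium calls for a xanthine oxidase inhibitor 2 to 3 days ahead, chemistries at baseline, 6-8 hours and 24 hours, and review of the 24-hour result before the next dose. In Low the inhibitor depends on a raised uric acid, there is no 6-8 hour sample, and the 24-hour repeat depends on creatinine above 1.4 or a raised uric acid. A patient with a larger lesion can therefore be assigned less protection than one with a smaller node.

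**Working it through.** The plan gives no figure to reproduce here, so the check applies the rules as written.

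**Tier rules** (s = largest lesion in cm; L = lymphocytes in 10⁹/L, with 25,000/mm³ = 25 × 10⁹/L; CrCl in mL/min)

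- High: s > 10, or (s > 5 and L > 25), or CrCl < 80 (6.3.1)
- Medium: (node and 5 ≤ s < 10), or L ≥ 25 (6.3.2)
- Low, literal: not High (6.3.3)
- Low, residual: neither High nor Medium

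**Single cases, all with L < 25 and CrCl ≥ 80**

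| Largest lesion | High? | Medium? | Tier (residual reading) |
|---|---|---|---|
| 5 cm node | no | yes | Medium |
| 9.9 cm node | no | yes | Medium |
| 10 cm node | no, needs > 10 | no, needs < 10 | Low |
| 9 cm extranodal mass | no | no, not a node | Low |
| 10.1 cm, either kind | yes | no | High |

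**Grid.** Two kinds (node, non-nodal) × six sizes (4, 5, 7, 9.9, 10, 10.1) × three lymphocyte counts (5, 25, 30) × three CrCl values (60, 80, 100) = 108 profiles.

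- High: 60. Medium but not High: 34. Neither: 14. Since 60 + 34 + 14 = 108, nobody falls outside the tiers.
- The 34 Medium profiles also satisfy the literal wording of Low.
- Of the 14 residual Low profiles, 4 have a 4 cm lesion and 10 have a lesion of 5 cm or more. The 10 are 2 with a 10 cm node (CrCl 80 or 100) and 8 with a non-nodal mass (5, 7, 9.9 or 10 cm, at CrCl 80 or 100). All have L = 5.

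A separate grid of 320 profiles with other values shows the same pattern: 0 uncovered, 56 both Medium and literal Low, and 24 with a 5 to 10 cm lesion in Low only. These counts show which combinations are affected. They depend on the grid and are not patient frequencies.

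**Step-up doses.** The starting dose is 4 mg, the dose table goes only downward, and re-escalation is barred. The number of possible step-up doses is 0.

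**Pre-dose chemistry over 12 cycles** (12 × 3 = 36 doses, none missed)

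- Low: each dose, 36 of 36.
- Medium: baseline at dose 1, then the sentence on subsequent doses, 1 + 35 = 36 of 36.
- High, from 6.3.1: dose 1 (baseline) and dose 2, so 2 of 36.
- High, adding the metabolic panel (CMP) rows in 11.3: Cycle 1 Days 1, 8 and 15 (3), plus Day 1 of Cycles 2 to 12 (11), so 3 + 11 = 14 of 36.
- Remainder for High: Days 8 and 15 of Cycles 2 to 12, 2 × 11 = 22. These are reached only by the TLS assessment row in the medication table and its footnote A, which asks in general terms for chemistries to be monitored.

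**The case against.** **Low as the remainder.** Section 6.3.3 follows High and Medium and opens as a residual category, so most readers would exclude Medium patients from it. That is fair, and the 34 double-classified profiles disappear on that reading. The 10 large-lesion profiles do not; the residual reading is what sends them to Low.

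**Masses may be nodal.** The Lugano criteria in 11.4 speak of nodal masses and count tonsils, Waldeyer's ring and spleen as nodal tissue, so the mass in inclusion criterion 3 need not be extranodal. This narrows the mismatch. It does not remove it, because patients with mainly extranodal disease are not excluded. The 10 cm boundary fails for nodes as well.

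**Footnote A in 11.3.** It applies to all patients, calls for prophylaxis suited to risk, and asks for more intensive measures as risk rises. An investigator could use it to escalate care for a 9 cm extranodal mass. It also reaches every ixazomib dosing day through the TLS assessment row, so High-risk patients are not left unmonitored. Both points stand as mitigation. But the footnote leaves the grading of risk open, and the 6.3 tiers are where the protocol grades it. The footnote does not state a pre-dose requirement either.

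**Blank cells.** The empty CMP cell for Cycle 2 onward does not show that the test is omitted: the CBC cell is empty too, yet the main schedule requires both on Day 1 of every cycle. Accepted; the 14 of 36 already counts those Day 1 panels.

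**Conclusion.** The concern holds as a wording error in operative safety rules, at minor severity. Coverage is complete, but a 10 cm lesion of any kind, or a non-nodal mass of 5 to 10 cm, with lymphocytes below 25 × 10⁹/L and CrCl of at least 80 mL/min is assigned to Low while a 5 cm node with the same laboratory values is Medium. The step-up bullet never operates, and section 6.3.1 has no working pre-dose rule for High after the second dose. That tier takes in every eligible patient with CrCl from 30 to below 80 mL/min, whatever the tumour burden.

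The High-risk gap is small and falls on later doses: 22 of 36 lack an explicit pre-dose panel but are covered by the general TLS row. The dose count assumes 12 full cycles; ixazomib may continue beyond that. How many of the 24 patients are affected cannot be derived from the documents. Confidence is high about the wording; actual loss of protection depends on how far the site's judgement overrides the text. Sample size, error rates and the primary analysis are unaffected.

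**What to change.** - In 6.3.3, define Low as meeting neither the High nor the Medium criteria, and state that the highest applicable tier governs.
- In 6.3.2, replace the lymph-node term with the lesion term used in 6.3.1.
- Close the 10 cm boundary, either by making High 10 cm or more or by letting Medium include 10 cm. This is a clinical choice for the investigator; the first option adds a hospital stay of at least 24 hours for the first dose.
- In 6.3.1 and 6.3.2, require pre-dose chemistries at each dose instead of each step-up, and fill the CMP row of the medication table in 11.3 for Cycle 2 onward to match.

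The cost is a wording amendment. Patients moved up from Low would have either 6-8 hour and 24-hour first-dose laboratory tests or the short stay. High-risk patients would have up to 22 more chemistry draws over 12 cycles, fewer if these are already taken under the TLS row.
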